11.2.4. Demography and Other Baseline Data

Demographic data and patient characteristics at screening/baseline will be listed and summarized by treatment group for all randomized patients using descriptive statistics.

Past and current medical history will be summarized by treatment group using the system organ class (SOC) as coded using the Medical Dictionary for Regulatory Activities (MedDRA) coding dictionary.

Past medical conditions will be defined as an onset date prior to randomization (Visit 2) and resolved (not on-going) as of Visit 2. Current medical conditions, defined as an onset date on or after the date of randomization (Visit 2) or an onset date prior to randomization (Visit 2) and unresolved (on-going) as of Visit 2, will be reported separately, but similarly to the past medical conditions. If both a past and a current (on-going) medical condition record are indicated for a condition, the condition will be presented under current medical conditions only.

11.2.5. Study Medication

The number of subjects at each visit will be summarized by treatment group.

The compliance to study medication, as recorded in the CRF, will also be summarized by treatment group. The proportion of subjects who are significantly noncompliant in the double-blind phase will be summarized by treatment groups.

11.2.6. Prior/Concomitant Therapy

Any medications or therapy present before the first dose of study medication (Visit 2) will be considered as prior medications. Concomitant medications (medications present while on study medication) will be recorded throughout the study and at early discontinuation. These medications will be coded using the WHO-drug dictionary. The number of subjects from the

Safety Population using prior or concomitant medications will be categorized by the WHO-drug category and preferred term, and presented for each treatment group. In any given category (e.g., drug category) a subject will be counted only once.

11.3. Efficacy Data Analysis

11.3.1. Primary Outcome

The primary efficacy outcome measure is the change from baseline in the Young Mania Rating Scale (YMRS) total score at Week 4. The primary statistical method will be mixed effect model repeat measurement (MMRM). A detailed description of the primary analysis model, and other supportive analyses will be included in the SAP.

As stated previously, any changes in the statistical methods that occur prior to database lock will be documented in the SAP and will not require a protocol amendment.

11.3.2. Secondary Outcomes

The other secondary efficacy outcomes include:

- Responder
- CGI-S
- CGI-C
- MADRS

These outcomes will be analyzed similarly as the primary outcome. The categorical endpoints will be analyzed by a Cochran-Mantel-Haenszel test with adjusting for sites.

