1. SYNOPSIS

Name of Sponsor/Company: Vanda Pharmaceuticals Inc.

Name of Investigational Product: iloperidone

Name of Active Ingredient: iloperidone, VYV-683

Title of Study: A multicenter, randomized, double-blind, placebo-controlled study to evaluate the efficacy and safety of iloperidone for 4 weeks in the treatment of patients with acute manic episodes associated with Bipolar I Disorder

Study center(s): Approximately 50 sites across the U.S. and Europe

Studied period (years):

Phase of development:

Estimated date first patient enrolled: March 2021

Phase III

Estimated date last patient completed (through the Short-Term

Treatment Phase): May 2022

Number of patients (planned): 400 (200 iloperidone and 200 placebo)

Diagnosis and main criteria for inclusion:

- Meet the *Diagnostic and Statistical Manual of Mental Disorder, Fifth Edition* (DSM-5) diagnosis of bipolar I disorder, manic or mixed type, as confirmed by the Structured Clinical Interview for Diagnostic and Statistical Manual of Mental Disorders, Fifth Edition (SCID) manic or mixed type with or without psychotic symptoms
- Men and women between the ages of 18-65 years inclusive
- Had at least one prior documented manic or mixed episode (with or without psychotic symptoms) that required treatment prior to screening
- Patients with Young Mania Rating Scale (YMRS) total score ≥ 20
- Patients with ≥ 4 on at least 2 of 4 YMRS items (irritability, speech, content, disruptive/aggressive behavior)
- Patients with Montgomery-Asberg Depression Rating Scale (MADRS) total score < 18
- Voluntarily hospitalized for current manic episode

Main Exclusion Criteria:

- Patients with a DSM-5 diagnosis other than bipolar I disorder that was the primary focus of treatment within the previous six months
- Patients experiencing a first manic episode or meeting criteria for rapid cycling

Investigational product, dosage and mode of administration:

Iloperidone will be provided as overencapsulated tablets containing either 1, 3, 6, 9, or 12 mg.

Duration of treatment:

Short Term Double-Blind Treatment Phase (4 weeks)

Titration Period – 1 week

Double-Blind Treatment Period – 3 weeks

Optional Open-Label Extension Phase (52 weeks)

Open-label Titration Period – 1 week

Open-label Extension Period – 51 weeks

Reference therapy, dosage and mode of administration:

Placebo will be provided in size and appearance that are visually identical to those containing iloperidone.

Primary Objective:

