To evaluate the efficacy of iloperidone monotherapy compared to placebo in the treatment of adult patients with bipolar I disorder experiencing an acute manic or mixed episode as measured by reduction in the Young Mania Rating Scale (YMRS) total score at Week 4

Secondary Objective(s):

- To evaluate the efficacy of iloperidone monotherapy compared to placebo in the treatment of adult patients diagnosed with bipolar I disorder experiencing an acute manic or mixed episode as measured by improvements in the Clinical Global Impression of Severity (CGI-S)
- To evaluate the efficacy of iloperidone monotherapy compared to placebo in the treatment of adult patients diagnosed with bipolar I disorder experiencing an acute manic or mixed episode as measured by reduction in the Young Mania Rating Scale (YMRS) total score at each trial visit
- To assess the rate of YMRS responders. A YMRS responder is defined as at least a 50% decrease from baseline in YMRS total score
- To assess the efficacy of iloperidone monotherapy compared to placebo in improving clinical symptomatology in adult patients diagnosed with bipolar disorder, manic or mixed episodes after acute treatment as measured by CGI-C
- To assess the efficacy of iloperidone monotherapy compared to placebo in improving clinical symptomatology in adult patients diagnosed with bipolar disorder, manic or mixed episodes after acute treatment as measured by MADRS
- To assess the safety and tolerability of iloperidone compared to placebo in the treatment of adult patients in an acute manic or mixed episode of bipolar I disorder as measured by changes in vital signs and weight, laboratory analytes, electrocardiograms (ECGs), and the incidence and severity of TEAEs and extrapyramidal symptoms (EPS) using the Barnes Akathisia Scale, Simpson-Angus Scale, and the AIMS

Exploratory Objective:

• To conduct a whole genome association scan to identify potential markers of response and safety for a bipolar indication

Open-label Extension (OLE) Objective:

• To explore the long-term safety and tolerability of dosing with iloperidone over an additional 52 weeks of treatment

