Subjects who complete the Double-Blind Treatment Period will be eligible to participate in the optional OLE Phase. Eligible subjects will enter the 7-day OLE Titration Period where iloperidone will be titrated to 24 mg/day total daily dose given as a bid regimen (12 mg bid). The target dose for CYP2D6 poor metabolizers is 12mg/d (6 mg bid). Subjects will then enter the OLE Maintenance Period in which subjects will be treated with iloperidone for up to 52 weeks.

Criteria for evaluation:

Mean baseline-to-endpoint change in total score using following parameters:

Efficacy:

- Young Mania Rating Scale (YMRS)
- Overall and mania severity of illness for Clinical Global Impression of Severity (CGI-S)
- Clinical Global Impression of Change (CGI-C)
- Montgomery-Asberg Depression Rating Scale (MADRS)

Safety:

- Adverse Events (AEs) and proportion of patients withdrawing due to AEs
- EPS scale scores as measured by Simpson-Angus Scale (SAS), Abnormal Involuntary Movement Scale (AIMS), and Barnes Akathisia Rating Scale (BARS)
- Metabolic risk factors, clinical chemistry, hematology, vital signs, and weight
- Columbia Suicide-Severity Rating Scale (C-SSRS)
- CYP2D6 genotyping
- 12-lead electrocardiograms (ECG)

Statistical methods:

If not otherwise specified, statistical significance is defined as $p \le 0.05$ and is two-tailed when appropriate. Data base lock will occur after 4-week ST double-blind period. The primary efficacy variable is the change from baseline in the YMRS total score.

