11. STATISTICAL PLAN

11.1. Sample Size and Accrual

Based on a two-sided t-test with the 5% significant level, the planned sample size of 200 subjects per arm (a total of 400 subjects) provides around 90% power to detect a mean difference of 3.6 in YMRS (change from baseline at week 4) assuming a standard deviation of 11 in each treatment group.

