11.2. Statistical Methods

This section describes the planned statistical analyses in general terms. A complete description of the methodology will be specified in a statistical analysis plan (SAP), which will be finalized prior to unblinding. Any changes in the statistical methods described in this protocol that occur prior to unblinding will be documented in the statistical analysis plan and will not require a protocol amendment.

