11.2.1. General

Statistical analyses will be performed using two-sided tests at alpha level of 0.05.

Data will be summarized by treatment group (and by visit when applicable), with respect to demographic and baseline characteristics, efficacy variables, and safety variables.

Summary statistics will include the mean, N, standard deviation, median, minimum, and maximum values for continuous variables, and frequencies and percentages for categorical variables.

For the analyses of change from baseline, only patients with a baseline and at least one post-baseline measure will be included in the analysis. Unless otherwise specified, baseline is defined as the latest non-missing observation across all the visits in the screening phase, before the active study drug begins. Endpoint will be the latest non-missing observation across all the post-baseline visits in the treatment phase.

Low enrolling sites will be pooled for analysis and the pooling algorithm will be determined prior to breaking the blind. The goal of pooling low enrolling sites is to have a sufficient number of patients per treatment group within a site for the analysis models. Unless otherwise specified, the pooled sites will only be used in the analyses where the site has an effect. The actual sites rather than the pooled sites will be specified in the data listings.

Details of the model and the analyses will be specified in the SAP. All statistical analyses will be performed using SAS®, Version 9.1.3 or higher.

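### Does the YMRS responder comparison need a change to the plan because no rule is stated for patients without a Week 4 score?

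*Combined protocol and SAP*

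**What the plan says.** The synopsis gives the threshold and no visit: "A YMRS responder is defined as at least a 50% decrease from baseline in YMRS total score". Section 11.3.2 then covers the responder rate, CGI-S, CGI-C and MADRS together: "These outcomes will be analyzed similarly as the primary outcome. The categorical endpoints will be analyzed by a Cochran-Mantel-Haenszel test", with adjustment for site. The primary outcome to which it refers is set in Section 11.3.1 as YMRS change at Week 4, analysed by MMRM.

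Two other places bear on the point. Section 11.2.1, in a paragraph on change-from-baseline analyses, says: "Endpoint will be the latest non-missing observation across all the post-baseline visits in the treatment phase". The synopsis heads its evaluation criteria "Mean baseline-to-endpoint change in total score using following parameters" and later writes "The primary efficacy variable is the change from baseline in the YMRS total score" without a time point.

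On where the detail belongs, Section 11.2 says: "A complete description of the methodology will be specified in a statistical analysis plan (SAP), which will be finalized prior to unblinding". Sections 11.2.1 and 11.3.1 repeat the deferral for the models. The text available here consists of the synopsis and Section 11.

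**The concern.** An MMRM uses the early visits of a patient who leaves, so it can target Week 4 without a Week 4 value for everyone. A Cochran-Mantel-Haenszel (CMH) test cannot; it takes one yes or no per patient. An instruction to analyse the secondaries like the primary therefore does not say how an early leaver is classed. Such patients are to be expected, because Section 11.2.2 admits to the Intent-to-Treat set anyone treated who has a single efficacy assessment after baseline, and Section 11.2.3 plans to tabulate discontinuations by reason.

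Three rules come to mind: test only patients with Week 4 data, use the last observation, or count a missing value as non-response. They can give different results from the same data. If dropout differs between arms, the responder result could depart from the primary result because of the rule chosen. There is also the worry that a rule left open might be picked once discontinuation patterns are known.

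**Working it through.** **1. The plan's own figure.** Inputs from Section 11.1: 200 per arm, difference 3.6, SD 11, two-sided 5%.

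- SE = 11 × √(2/200) = 1.1
- 3.6 / 1.1 = 3.27
- Power from the noncentral t with 398 df = 0.904

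The stated figure of around 90% reproduces. It concerns the continuous primary outcome, so the responder rule does not enter it.

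**2. What the text fixes.** The primary objective in the synopsis, Section 11.1 and Section 11.3.1 all name Week 4, so the synopsis sentence without a time point cannot mislead. For responder status, Section 11.3.2 points to Week 4 by analogy. Section 11.2.1 could also supply a status, since a 50% decrease is derived from change from baseline. The text thus offers two readings. Counting missing as non-response is a common convention with no basis in the text.

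**3. Can the rule matter with a drug effect?** All rates are assumptions: 55% v 40% responders among completers, 20% v 10% at last observation among dropouts, 200 per arm, no site strata. Non-responder rate = completer rate × (1 − dropout). The last-observation rate adds dropout × dropout response. For 35% dropout on iloperidone and 25% on placebo:

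- Non-responder: 0.55 × 0.65 − 0.40 × 0.75 = 0.3575 − 0.3000 = 5.75 points
- Last observation: (0.3575 + 0.20 × 0.35) − (0.3000 + 0.10 × 0.25) = 0.4275 − 0.3250 = 10.25 points

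| Dropout, iloperidone / placebo | Week 4 only | Last observation | Non-responder |
|---|---|---|---|
| 20% / 20% | 15.0 points, power 77% | 14.0, 82% | 12.0, 70% |
| 35% / 25% | 15.0, 71% | 10.25, 56% | 5.75, 23% |
| 25% / 35% | 15.0, 71% | 16.75, 94% | 15.25, 90% |

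**4. Can it matter without a drug effect?** This was a simulation of 200 per arm. The synopsis gives "Approximately 50 sites across the U.S. and Europe", hence 400/50 = 8 patients per site. Assumed: baseline YMRS mean 29, SD 5, floor 20; weekly mean changes −5, −9, −12, −14 with SDs 7, 9, 10, 11; correlation 0.75 to the power of the lag; dropout after weeks 1 to 3; YMRS-driven dropout with logistic slope 1.5 per SD of less improvement. The first four rows use 4,000 trials each; two independent reruns of 3,000 trials each agreed with them within 3 points. The last three rows use the same model with milder asymmetry. Entries are rejection rates of the site-stratified CMH test at nominal 5%.

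| Dropout, iloperidone v placebo | Week 4 only | Last observation | Non-responder |
|---|---|---|---|
| A: 20% v 35%, unrelated to YMRS | 5.0% | 11.7% | 33.6% |
| B: 30% unrelated v 30% driven by poor YMRS | 27.0% | 5.1% | 24.0% |
| C: 20% unrelated v 35% driven by poor YMRS | 35.6% | 13.1% | 5.4% |
| D: 30% v 30%, same mechanism | 5.4% | 4.7% | 5.0% |
| 30% v 30%, slopes 1.0 v 1.5 | 5.9% | 5.2% | 6.0% |
| 25% v 30%, same mechanism | 6.2% | 6.3% | 6.4% |
| 25% v 30%, unrelated | 4.8% | 5.4% | 8.1% |

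**5. Reading the large entries.** In A the true Week 4 response is 48.3% in both arms. Non-responder counting gives 48.3% × 0.80 = 38.6% and 48.3% × 0.65 = 31.4%, a gap of 7.2 points that is entirely retention. If response means improving and staying in the study, that gap is a real difference between randomised arms. It is false only if the question is response had everyone stayed.

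**The case for a change.** The strongest case for a change is that the gap is real and cheap to close. No sentence ties responder status to a visit or classes a patient who lacks that value, and the last-observation endpoint in Section 11.2.1 does not mention responders. Each rule fails under at least one of patterns A to C. Multiple imputation of Week 4 YMRS within arm, followed by the 50% cut, gave rejection of 3.7% to 4.6% in patterns A to D and spurious differences within 0.1 points. In a companion illustration with a 3.6-point effect and 30% control-arm dropout, its responder power was 63% and 62% under two dropout mechanisms, at most about 2 points below the best alternative.

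The observation that the text leaves the choice open stands. The step to a change does not. B and C set dropout wholly unrelated to YMRS in one arm against steep YMRS-driven dropout in the other; milder patterns bring every rule to between 4.8% and 8.1%. The imputation did well partly because the data were generated under its own missing-at-random assumption. It was also tested as an unstratified difference, not in the site-adjusted form that would replace the planned test. Imputation and non-responder counting answer different questions, and competent statisticians choose either.

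The worry about a late choice is met by the order of events in Section 11.2. Dropout by arm, which drives A to C, should not be known while the blind holds.

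The wording points change no result. On the inference from its name that CGI-C has no baseline score, the baseline requirement in Section 11.2.1 does not reach it, since that requirement covers change-from-baseline analyses only.

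**Conclusion.** No change to the plan follows. Sections 11.2 and 11.3 describe the methods in outline and assign the detail to the SAP. The responder visit and the class of patients without that value are the kind of detail an analyst settles there, most naturally at Week 4 to match the primary. No stated rule is shown to give a wrong result, and preferring imputation over non-responder counting is a choice of question, not a correction.

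The effect on the responder result cannot be sized from the documents. Under assumed dropout it ranges from none, when the arms drop out alike, to a rejection rate of about 36% under strong asymmetry. The primary analysis, the sample size of 400 and the power of about 90% are unaffected. The conclusion assumes that the SAP names the visit and the classification before unblinding, as Section 11.2 promises for the methods as a whole.

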Overall Design: This will be a multicenter, randomized, double-blind, placebo-controlled, parallel-group study. The study has two phases: the Pre-Randomization Phase and the Short-Term Treatment Phase and is followed by an optional third phase, the Open-Label Extension (OLE) Phase. The Pre-Randomization Phase includes the Screening visit and the Baseline visit. The Short-Term Treatment Phase includes two periods: (1) the Titration Period and (2) the Double-Blind Treatment Period. The optional OLE Phase also includes two periods: (1) the OLE Titration Period and (2) the OLE Maintenance Period.

The Pre-Randomization Phase begins with the screening visit (Day -7 to -1) during which an informed consent will be obtained from potential patients and their eligibility will be initially assessed. The Screening Visit (Day -7 to -1) and Baseline Visit (Day 0) will be separated by a maximum of 1 week. Patients meeting all entry criteria for enrollment into the study will enter the Short-Term Treatment Phase. During this Phase, patients will undergo a 7-day Titration Period where iloperidone or placebo will be titrated to 24 mg/day total daily dose given as a bid regimen (12 mg bid) utilizing a fixed titration regiment, whereby the doses will be increased to $2\rightarrow 6\rightarrow 12\rightarrow 18\rightarrow 24\rightarrow 24\rightarrow 24$ mg/day (bid doses of 1, 3, 6, 9, 12, 12, and 12 mg). The target dose for CYP2D6 poor metabolizers is 12mg/d (6 mg bid) utilizing a fixed titration regiment, whereby the doses will be increased to $2\rightarrow 6\rightarrow 12\rightarrow 12\rightarrow 12\rightarrow 12\rightarrow 12\rightarrow 12$ mg/day (bid doses of 1, 3, 6, 6, 6, 6, and 6 mg). Patients will discontinue current antipsychotic treatment prior to the first day of the Titration Period (Day 1-7). Patients will remain in-patient during this period to ensure compliance with dosing.

Subjects continuing to meet the criteria for randomization will be eligible to proceed to the Double-Blind Treatment Period. During this period, patients will be randomized 1:1 to either iloperidone or placebo, stratified by country. Subjects will remain in this period for up to 3 weeks.

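### Does adjusting the responder test for sites, when randomization was stratified by country, weaken the categorical secondary analyses?

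*Combined protocol and SAP*

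**What the plan says.** The Overall Design part of the synopsis gives one stratification factor: "patients will be randomized 1:1 to either iloperidone or placebo, stratified by country". The trial is planned at "Approximately 50 sites across the U.S. and Europe", with 400 patients.

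YMRS response is a secondary objective ("To assess the rate of YMRS responders"), defined as a fall of at least half from baseline, so it is binary. Section 11.3.2 names the test for such outcomes: "The categorical endpoints will be analyzed by a Cochran-Mantel-Haenszel test with adjusting for sites".

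Section 11.2.1 (General) adds: "Low enrolling sites will be pooled for analysis and the pooling algorithm will be determined prior to breaking the blind". It gives the purpose, which is enough patients per arm in each site stratum for the models to work, and reserves the pooled sites for analyses in which site plays a part. The pooling rule and the model details are left to the SAP, which Section 11.2 says will be final before unblinding. Section 11 does not mention country.

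**The concern.** A common rule is to analyse as one randomized: a factor used to stratify the allocation should reappear in the analysis. Here the allocation uses country and the test uses site, so the factor seems to have been dropped and replaced by a much finer one.

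The finer factor has a price. At about 8 patients per site, with balance planned only at country level, chance imbalance within sites wastes information in a Cochran-Mantel-Haenszel (CMH) test. Pooling reduces the waste, but no minimum pool size is given, and nothing says pools must stay inside a country. Pools spanning countries would cut across the randomization strata. At stake would be precision for the responder comparison.

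**Working it through.** **Inputs from the documents.** N = 400, 1:1; about 50 sites, so 400/50 = 8 per site; stratification by country; two-sided 5%.

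**Assumed, because the documents do not give them.** Number of countries (6 unless stated), blocks of 4, response rates, minimum pool size, and the spread of response between sites and between countries.

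**1. The plan's own figure.** Section 11.1 says the sample size "provides around 90% power to detect a mean difference of 3.6 in YMRS", with SD 11. The standard error is 11 × √(2/200) = 1.10; 3.6/1.10 = 3.273; 3.273 − 1.960 = 1.313; power = Φ(1.313) = 90.5%. This reproduces. It concerns YMRS change; no power is claimed for response.

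**2. Is country really left out?** Each site belongs to one country. A CMH test compares arms only within strata, so within-site comparisons are also within-country comparisons. The same holds for pools formed inside a country. If a pool did span countries, the 1:1 ratio is the same in every country, so country would still not be confounded with treatment.

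**3. Information lost by finer strata.** CMH information is proportional to the sum of n₁n₀/n over strata. With K strata nested in C countries, the expected loss against country strata is about (K − C)/(N − C).

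- Unpooled, K = 50, C = 6: 44/394 = 11.2% (simulated: 11.2% with equal sites). For C = 2 to 8 the formula gives 12.1% to 10.7%.
- Pools of at least 10 patients, about 29 strata: 23/394 = 5.8% (simulated 4.9-5.8%).
- At least 15, about 19 strata: 13/394 = 3.3% (simulated 3.1-3.4%).
- At least 20, about 15 strata: 9/394 = 2.3% (simulated 2.0-2.3%).
- At least 30: about 1% (simulated).

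Since the plan pools, the lower rows apply.

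**4. In power.** At assumed response rates of 35% and 50% with 200 per arm, power is 86.1% with no loss, 85.5% at 2%, 84.4% at 5% and 81.4% at 12.3% (50 sites against no stratification). Pooling therefore costs about 0.6 to 1.7 points. This calculation assumes that sites do not differ in response; where they do, adjusting for site recovers power.

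**5. Country strata against site strata when sites may differ.** Simulated power (%), uneven enrolment, 35% against 49% responders, pool minimum 16:

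| Spread of response (logit SD) | Country | Pooled within country | Pooled across countries | Unpooled | Country minus within-country pools |
|---|---|---|---|---|---|
| None | 81.2 | 80.3 | 79.8 | 77.1 | +0.9 |
| Site 0.5 | 81.3 | 81.4 | 81.3 | 79.6 | −0.1 |
| Site 1.0 | 82.6 | 84.5 | 84.1 | 84.6 | −1.9 |
| Country 1.0, site 0.25 | 87.0 | 86.2 | 83.6 | 83.9 | +0.8 |

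Monte Carlo error is 0.4 to 0.6 points per power figure. A repeat gave differences of +0.8, +0.3, −1.8 and +1.1. With equal sites and no site differences the gap was 80.6 − 78.6 = +2.0.

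**6. Pools that ignore country.** Against within-country pools they lose 0.5, 0.1, 0.4 and 2.6 points in the four rows. Against country strata, the last row loses 87.0 − 83.6 = 3.4.

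**7. Validity.** Simulated type I error was 4.7-5.1% in one set of runs and 4.4-5.6% in another (simulation standard error about 0.35 points in the latter), including pools that cross countries.

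**The case for a change.** The best case for the concern is that Section 11.3.2 does not defer its adjustment factor: it names site. The plan gives no pool size and no bar on pooling across countries, and does not say outright that the CMH test uses pooled rather than actual sites. In a trial spanning the U.S. and Europe, country differences are plausible. When pooling ignored country in the simulation, 62% of pooled strata contained more than one country. Naming the strata would cost a sentence or two.

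Much of this is factually right. The silence on pool size and country boundaries is real, and a line on them in the SAP would be good housekeeping. But the algorithm is expressly to be fixed before unblinding and has a stated aim; a detail assigned to a later document is not an error here. The natural reading of Section 11.2.1 is that a site-adjusted test is where pooled sites are used. Nothing says pools will cross borders, and the test stays valid if they do. The case for country over site also fails as a general rule: where sites differ strongly, country strata lose about 2 points against within-country pools.

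**Conclusion.** The concern does not hold. Site is nested in country, so a CMH test on sites, or on pools kept within a country, respects the stratified randomization. Type I error is near 5% in all variants. The 11-12% loss belongs to an unpooled analysis that the plan does not intend. With pool minimums of 10 to 20 patients the loss is about 2-6%, or about 1 to 2 power points on a secondary endpoint.

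Whether country or site is the better stratum depends on unknown heterogeneity. With uneven enrolment the simulated difference runs from +0.9 to −1.9 points, and reaches +2.0 with equal sites and no site differences. That is a choice on which experienced statisticians can differ. The loss of about 3 points needs two assumed conditions together: pools across countries and strong country differences.

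The sizes rest on assumed numbers of countries, block size, response rates, pool sizes and heterogeneity. The nesting argument does not depend on these. Nothing here bears on the MMRM, whose covariates Section 11.3.1 leaves to the SAP.
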